Impact of Lifetime Exposure to Air and Noise Pollution on Cardiovascular Disease and Mortality - the AIRCARD Study.

NCT04353232

17/10/2023

Impact of Lifetime Exposure to Air and Noise Pollution on Cardiovascular Disease and Mortality - the AIRCARD Study.

INTRODUCTION

The purpose of this study is to determine the impact of individually lifetime accumulated exposure to air and noise pollution on the incidence and prevalence of cardiovascular diseases (CVD) and mortality.

Air as well as noise pollution have harmful effects on human health (1). Experimental and clinical studies have shown a strong impact between particulate matter (PM_{2.5}) and cardiovascular disease (CVD) (2, 3). Prolonged exposure to PM_{2.5} has been associated with the development of atherosclerosis and adverse cardiovascular events. However, also short-term exposure has been linked to acute coronary events (4, 5). PM_{2.5} is, however, a combination of many components of specific pollutants that have a size of two and a half microns or less in width. However, there is a knowledge gap, as investigation into which specific components of air pollutants that contribute the most to the development of CVD is lacking. There is a need to adopt and encourage preventive measures but also put in place environmental policies that are effective in promoting the reduction of exposure to pollutants. We want to aid in this shift by showing which specific pollutants contribute the most to the development of CVD so that we can better target these specific air pollutants for better prevention initiatives.

We will determine the contribution of sulfate, nitrate, ammonium, elemental carbon, organic carbon, silicon, or sodium ion, all contained in PM_{2.5}, to CVD. More relevant is that we can demonstrate which pollutants emitted from power plants, industries, and automobiles have the worst impact. We can provide insightful information to decision- and policymakers and this can help better target interventions against harmful pollution discharges and hereby significant prevention of many diseases with special emphasis on CVD and mortality.

The results from our pollution study can be implemented immediately when new roads, buildings or industries are planned as well as aid industries in limiting their pollution burden and aid government officials in making new legislative regulations on air pollution. This will have an impact on the general health of the population and therefore for every individual and at all decades of life. The results will have a huge impact within both clinical research, prevention, and the broader public health not only in Denmark, but globally.

From a societal perspective, it is already known that socioeconomic status, personal health, and housing is correlated (6). The Danish Health Authority reported that cardiovascular death can be halved if people from the lowest socioeconomic classes have the same risk of developing CVD as people from the upper socioeconomic classes. If we confirm that air or noise pollution poses the risk as has been suggested, we will be able to bridge the gap created by social inequality in CVD if social inequality also relates to pollution.

BACKGROUND

Cardiovascular disease and its thrombotic complications are currently one of the deadliest and most disabling diseases; each year CVD causes 3.9 million deaths in Europe and loss of 26 million disability-adjusted living years in the EU (7). The occurrence of CVD is the effect of lifetime exposure to various risk factors (8, 9). Subclinical coronary artery disease as determined by revealing coronary artery calcification (CAC) has been shown to provide powerful prognostic

information beyond that of traditional Framingham risk factors across a wide range of ages and ethnicities (10-13). Social inequality is a known CVD risk factor and the Danish National Board of Health has reported that CVD carries the second largest socioeconomic difference in burden of disease, and if the people with lowest socioeconomic status had the same risk as those with the highest status, the rate of cardiovascular death would be reduced by half (14, 15). However, known genetic and environmental risk factors cannot explain all CVD prevalence, and there is an increasing need for population-based identification of novel risk factors (16).

In a previous study, we demonstrated that living in a city center contributes to the presence of calcification in the coronary arteries (17). Air pollution is a major environmental factor associated with health impacts (18, 19), which disposes significantly to the incidence and prevalence of CVD (20). Furthermore, epidemiological studies suggest that long-term exposure to air pollution (21-24) relates to progression of CAC.

Previous studies have shown an association between CVD and short-term exposure to increased air pollution levels. The literature on the impact of long-term effect of air pollution is, however, limited. A prospective 10-year cohort Multi-Ethnic Study of Atherosclerosis and Air Pollution (MESA Air) examined more than 7,000 men and women in the age of 45-84 years from six cities in the United States. Data from 5,000 US Environmental Protection Agency monitors and more than 7,420 MESA Air stationary location monitors in six MESA cities were collected with recent and 20-year historical exposure data from participants home addresses (23, 25). The MESA Air study found a strong association with accelerated atherosclerosis in the coronary arteries over a 10-year period related to air pollution (26). However, a limitation of the MESA Air study involves the collection of the air pollution data. The predicted air pollution data for each participant in the study was a collection of questionnaires, and the measurements were averaged data from a two-week period. Strengths in the MESA Air study are the repeatedly measured CAC with CT to evaluate the accelerated atherosclerosis in participants (25). It has also been reported in the German Heinz-Nixdorf Recall (HNR) study (27) and from Lambrechtsen J et al in the Danish DANRISK sub study (17) that CAC was higher in participants living near roads and in city centers, respectively. But the identity of the pollutants that carry the highest risk is unknown.

In Denmark, a unique temporal and spatial epidemiological model for retrospective calculation of accumulated individual air pollution exposure exists (28-32), and it is possible to calculate the air pollution retrospectively to 1979. These data include concentrations of atmospheric particles with diameter less than 2.5 μm (PM_{2.5}), which consist of several components. Furthermore, the model system calculates concentrations of health relevant gases, and nitrogen dioxide (NO₂), ozone (O₃) and sulfur dioxide (SO₂) (33, 34).

This study will provide more detailed data as we can model pollution levels hourly compared to the MESA Air's two-week periods. Furthermore, we will incorporate work addresses where previous studies are limited to home addresses only. The MESA Air study is the most comprehensive to date but limited as they divide the contributions into PM_{2.5} and NO_x only. Previous studies have provided air pollution data as an accumulated amount where we have the possibility to show if the air pollution is of local origin (e.g., traffic, wood stoves), national origin (e.g., power plants, industries, agriculture), or international origin (e.g., other countries, shipping). We can show which component contributes most and where the pollutant(s) comes from.

The American Journal of Hypertension released a call for clinical trials on the correlation between air pollution and CVD in 2018 (35), and a joint opinion was released in April 2021 by the World Heart Federation, American College of Cardiology, American Heart Association, and the European Society of Cardiology due to the increasing concern about air pollution in the development of cardiovascular disease (36). They state that *50% of the 6,7 million deaths that can be attributed to air pollution are due to CVD* (36), which is concerning due to the fact that the disease burden of air pollution seems to be “larger and higher-ranking” than some of the presently recognized CVD risk factors (37).

We published a method article in 2020 (38) accounting for the aims of our study and the release of the concerning joint opinion in Circulation has reinforced the importance of this study. Hence, this project will contribute with unique and precise data to show if a correlation between air pollution and CVD burden truly exists.

Another aspect of environmental risk factors is environmental noise. The first article about this subject was published in 1985, nevertheless, it is only in recent years we are seeing both growing quality and quantity of articles in esteemed

journals about environmental noise. These articles unanimously report an increased risk of hypertension, coronary heart disease, stroke, heart failure and atrial fibrillation with even slightly increased levels of environmental noise (specifically road traffic noise and aircraft noise). One of these studies (39) was a cross-sectional study of residents in London who lived close to Heathrow Airport. The study found an increased relative risk for admission due to coronary heart disease and CVD. Another study relating to another cardiovascular complication, hypertension, found that long-term residential exposure to noise was associated with increased incidence of (self-reported) hypertension (40).

HYPOTHESIS

The purpose of this study is to determine the impact of individually accumulated exposure to air and noise pollution, as well as exposure fluctuations (peaks), on the incidence and prevalence of CVD. Noise pollution can be a significant confounder for the relation investigated and we will therefore include accumulated data for noise over time together with air pollution data.

The ICD or SKS disease classification code system will be used to identify clinical events for patients from the two trials (described below). CVD mortality and total mortality as well as clinical events from myocardial infarctions, percutaneous coronary interventions, coronary artery bypass grafts, heart failure, apoplexies, and bypass will be examined. The analysis will be stratified by socioeconomic status to determine if there is a social inequality in the air and noise pollution impact.

We will examine the individual air pollution exposure as well as noise exposure to understand each pollutants' contribution to the accumulated risk and demonstrate the impact of air and noise pollution on CVD morbidity and mortality. We hypothesize that:

1. the amount of accumulated air as well as noise pollution is a highly independent significant risk factor for clinical CVD, when accounting for all traditional cardiovascular risk factors.
2. certain subdivisions of the air pollution exposure carry the highest contribution for development of clinical CVD. This will provide novel and valuable information as this has never been investigated with the precision we can deliver.
3. accumulated air and noise pollution from both individual home addresses and work addresses together better predicts clinical CVD than models based solely on home addresses. No study has evaluated this before.

Furthermore, the impact on the result of social inequality will be thoroughly examined.

METHOD

Project design

This study is designed as a prospective registry-based observational study using modelled air/noise pollution data. The population is predominantly males from two Danish clinical trials (DANCAVAS and VIVA trials)

Study population

DANCAVAS I and II (41-43) are two similar population-based randomized, multicentered, clinically controlled studies designed to evaluate the benefits of 7-step multiple cardiovascular screening and modern vascular prophylaxis in a population of men and a small subpopulation of females, aged 60-74 years, living in the southern part of Denmark. For each participant, all relevant CVD risk factors were measured or determined.

The screening included (figure 1): 1) low-dose non-contrast CT scan to detect CAC and aortic/iliac aneurysms, 2) ankle-brachial blood pressure index (ABI) to detect peripheral arterial disease (PAD) and hypertension, 3) a telemetric assessment of the heart rhythm, and 4) a measurement of the cholesterol and plasma glucose levels.

The Viborg Vascular (VIVA) screening trial (44) is a randomized, multicentered, population-based clinically controlled study designed to evaluate the benefits of vascular screening and modern vascular prophylaxis in men between 65-74 years of age living in the region of Mid Denmark (Viborg County). For each participant, abdominal ultrasound scanning of the infrarenal aorta were performed to detect abdominal aortic aneurism (AAA), and ABI were measured to detect PAD and hypertension (45). In all, 18,749 men were screened.

A total of 33,723 participants in the age of 60-74 are included from the two cohorts. In both trials, an AAA was defined as maximal infrarenal diameter of 30 mm or more, and PAD was defined as an ABI < 0.90 or ≥ 1.40 using the same validated hand held Doppler-based methodology (46). We have accounted for traditional CVD confounders in all participants. This is unique for our study. Previous studies on air pollution and CVD burden have not been able to prospectively consider these confounding variables to the same extent.

Air pollution

In Denmark a validated and reliable air pollution model system is available (figure 2). The system is named DEHM/UBM/AirGIS (28, 30-32) and consists of three coupled models; the Danish Eulerian Hemispheric Model (DEHM) (28, 32), the Urban Background Model (UBM) (29) and the Operational Street Pollution Model (OSPM) (30, 31) and a GIS system (AirGIS) that couples the modelled concentrations with the address level of the population. The system calculates air pollution concentrations of 80 chemical species as well as air pollution levels in cities, in streets and on address level even on both side of the street. These pollution levels can be calculated back to 1979 giving retrospectively data 40 years back. The model system is validated in relation to air pollution measurements throughout Denmark back to 1990 with high correlation between model estimated values and measured values (28, 30, 31, 47). This multi-scale model system is unique, capable of running on very high temporal (hourly) and spatial (address level) resolutions. The development of the models and the calculation of air pollution and measurements is performed at Aarhus University, Department of Environmental Science (ENVS). The model is robust; taking all necessary factors into account that could contribute to the individual life-long air pollution exposure and the model is one of the best in the world.

Noise pollution

Noise is calculated using state-of-the-art algorithms implemented in a well-known software, the SoundPLAN. The algorithms, reflecting advanced physics and mathematics-based knowledge, consider the propagation of sound in the atmosphere as well as the sound originating from the source, e.g., road transport, railway. Here, information from various national registers, such as the national traffic database, including traffic counts, travel speeds, the building register, the address register, and the Danish surface and elevation model, to name a few. In addition, advanced weather classes reflecting all meteorological conditions in Denmark are used in noise calculations. The model output is a noise estimate at the address location or any location of interest in Denmark, which can be subsequently used to investigate the health impacts of short-term and/or long-term noise exposure (48, 49).

Statistics

The entire study population is monitored until December 31. 2022, in the Danish national registers.

Primarily a multivariate Cox proportional hazards regression model will be used to examine the associations between air- and noise pollution and all-cause mortality and CVD morbidity and mortality when adjusting for inclusion date, sex, and other potential confounding factors at baseline.

Descriptive statistics of the main study variables to examine noise pollution will be presented in tables, frequencies with percentages of dichotomous/ordinal variables and medians with quartiles for numeric variables. Outcomes will be analyzed both as dichotomized variables, present CAC, severe CAC (CAC score above 400), AAA and PAD, and as the underlying continuous variables, CAC score, aortic diameter, and lowest measured ankle-brachial blood pressure index. Confounding CVD variables will be considered and adjusted for (e.g., lifestyle, medical history, QoL, weight,

height, waist circumference, blood pressure, ABI, calcium score for coronary arteries, aortic dimensions, HbA1c and lipid parameters).

To investigate hypothesis about noise we will, for each dichotomized outcome, estimate adjusted odds ratios using multivariable logistic regression, with cumulated noise pollution as exposure and the Framingham risk factors as confounders. The continuous variables will be analyzed in multivariable linear regression models and the cardiovascular risk factors as confounders.

To investigate the impact of work versus home address, we will compare regression models with accumulated air pollution from both work and home addresses with models with air pollution only from home addresses. ROC curves from both models will be compared to evaluate the hypothesis.

Ethics approval and consent

The DANCAVAS and VIVA studies were approved from “Videnskabsetisk Komité” (S20140028, S20160164 and M20080028). Access to the participants’ former residential addresses has been approved from “Sundhedsdatastyrelsen” (FSEID-00005213).

Feasibility

We have formed the group of researchers that will perform the study and we have received all the necessary approvals. The group includes professors in the areas where special skills are needed.

COLLABORATION

This project is a collaboration across disciplines and sectors (cardiology, physics, environmental sciences, surgery, public health). The study will be performed as a collaboration between:

- Cardiovascular Research Unit, Odense University Hospital - Svendborg; [name] and [name]

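### Stratifying by socioeconomic status does not by itself show whether the pollution effect is socially unequal; the protocol names no contrast between strata

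*Protocol*

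**What the plan says.** The Hypothesis section of the protocol names both a procedure and its purpose: "The analysis will be stratified by socioeconomic status to determine if there is a social inequality in the air and noise pollution impact". The only other statement on how this will be studied closes that section: "Furthermore, the impact on the result of social inequality will be thoroughly examined". The Introduction attaches a conditional societal benefit, that the study could help to "bridge the gap created by social inequality in CVD if social inequality also relates to pollution".

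The Statistics section describes the models. For the main analysis: "Primarily a multivariate Cox proportional hazards regression model will be used to examine the associations between air- and noise pollution and all-cause mortality", extended to cardiovascular morbidity and mortality, "adjusting for inclusion date, sex, and other potential confounding factors at baseline". For noise, logistic models are planned "with cumulated noise pollution as exposure and the Framingham risk factors as confounders", with linear models for the continuous outcomes. For work versus home addresses the section names a comparison: "ROC curves from both models will be compared to evaluate the hypothesis". It does not mention SES, and it names no exposure-by-SES term, no heterogeneity test and no ratio of stratum-specific estimates.

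**The concern.** Whether pollution harms one social group more than another is a question about effect modification. Its answer is a difference between effects, such as a ratio of hazard ratios with its interval. A set of stratum-specific hazard ratios, each with its own p-value, does not contain that quantity until someone forms the contrast.

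Without a named contrast, the easy reading is that an effect which is significant in one group and not in another is unequal. That reading can fail in two ways. Equal effects can look unequal because one stratum fell short of significance by chance. Unequal effects can look equal because every stratum is significant. Either error would bear on what the study says about social inequality.

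**Working it through.** **What each meaning of stratified delivers**

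- Separate models per SES group give one exposure estimate per group. A difference can be derived from them, but the protocol does not say that it will be.
- A Cox model with a separate baseline hazard per SES group and a common exposure coefficient gives no SES-specific effect at all.

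Under either meaning, the plan as written yields no estimate of the difference in effect between groups.

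**Inputs**

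- From the protocol: cohort size ("A total of 33,723 participants in the age of 60-74 are included from the two cohorts"). It gives no event count, effect size, significance level, power or number of SES groups, so there is no figure to reproduce.
- Assumed: two-sided 5% level, K equal strata, the same true effect in every stratum, 5% to 20% of participants with an event, and a hazard ratio (HR) of 1.00 to 1.10 per SD of exposure.

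**Step 1: chance that the strata disagree on significance**

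With power p in each stratum, P(at least one significant and at least one not) = 1 − p^K − (1 − p)^K.

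| Power p | K = 2 | K = 3 |
|---|---|---|
| 0.05 (no effect anywhere) | 10% | 14% |
| 0.50 | 50% | 75% |
| 0.80 | 32% | 48% |
| 0.90 | 18% | 27% |

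For K = 3:

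- p = 0.5: 1 − 0.125 − 0.125 = 0.75
- p = 0.8: 1 − 0.512 − 0.008 = 0.48
- p = 0.99: 1 − 0.9703 − 0.000001 = 0.030

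**Step 2: what power this cohort might have**

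The standard error of the log HR per SD is taken as 1/√(events per stratum). Power is Φ(ln HR/SE − 1.96) + Φ(−ln HR/SE − 1.96).

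- *10% with events, K = 3, HR 1.05.* Events per stratum are 33,723 × 0.10/3 ≈ 1,124, so SE = 0.0298. Then ln 1.05/SE = 0.0488/0.0298 = 1.64, power is 37%, and discordance is 1 − 0.37³ − 0.63³ ≈ 70%. The median chance ratio of the largest to the smallest stratum HR is 1.05, as large as the assumed effect. Comparing point estimates by eye is therefore no safer.
- *20% with events, K = 3, HR 1.10.* Events per stratum are about 2,248, SE = 0.021, power is 99%, and discordance is about 2%. This is slightly below the 3% in step 1 because the power is a little above 0.99 before rounding.

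**Step 3: a between-stratum contrast**

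A heterogeneity test uses Q = Σ(b_k − b̄)²/SE², referred to chi-squared with K − 1 degrees of freedom, where b_k is the log HR in stratum k. Simulated with equal true effects, it rejected in 4.8% to 5.1% of runs for every K from 2 to 5, every event rate and every HR tried.

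**Step 4: price in precision**

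The difference between two equal strata has SE = √2 × 0.0298 = 0.0422 in the first example. The 95% limits for a ratio of HRs lie a factor exp(1.96 × 0.0422) = 1.09 either side of the estimate. For a single stratum's HR the factor is exp(1.96 × 0.0298) = 1.06.

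**The case against.** The strongest reply is that the protocol is incomplete here rather than wrong. It does not say that inequality will be judged by stratum-wise significance, and it does not exclude an interaction test. A statistical analysis plan that is not shown could contain one. Separate strata hold different people, so a valid contrast can be computed from the stratum estimates and their standard errors. All of this stands. A reader might infer that the study will judge inequality from significance within strata alone. The text does not support that, because the inference rests on silence.

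The discordance figures belong to a decision rule that the protocol never states, at powers that it never gives, and they nearly vanish when every stratum is very well powered. That also stands.

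A reader might also take social inequality for a headline conclusion. It is not among the three numbered hypotheses, and the Introduction's sentence is conditional. That sentence could refer to unequal exposure rather than an unequal effect, and the closing sentence of the Hypothesis section could refer to confounding. Neither carries the point, which rests on the sentence about stratification.

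Finally, a single product term holds confounder effects equal across SES groups, which separate models do not, and a Cox term alone would leave out the logistic and linear noise models. Both are fair, and the fix allows for them.

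The reply does not remove the mismatch. The protocol names a procedure as the means of deciding a question, and that procedure stops one step short of the answer. The Statistics section does name a comparison for work versus home addresses and gives none for SES.

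**Conclusion.** The point holds as a gap between a stated method and its stated purpose, in a secondary aim. It should be closed, but it does not touch the main analysis of pollution and outcome.

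Its size is conditional. If conclusions followed stratum-wise significance, the chance of an apparent inequality with equal effects in three strata would run from 2–3% (power about 99%) through 48% (80%) to 75% (50%), against 5% for a test of interaction. These figures rest on equal strata, a 5% level and assumed power. That the contrast is missing from the protocol rests on none of these assumptions.

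**What to change.** Add to the Statistics section, or point there to the analysis plan if it already says so:

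- The conclusion on social inequality, as a secondary aim, rests on a pre-specified exposure-by-SES interaction estimate with its 95% CI.
- The estimate comes from a product term, with SES also in that model as a main effect, or from an equivalent heterogeneity contrast of the stratum-specific estimates.
- This applies to the Cox models and to the logistic and linear noise models, wherever an SES difference is claimed.
- Stratum-specific estimates are shown as description.

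The cost is a short addition to the text and one more term or contrast per model, with no new data. The downside is a wider confidence interval for the contrast than for a single stratum, which reflects the real uncertainty of the question asked.

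### In the noise prevalence models, AAA and PAD rest on the screening diameter and ABI alone, so participants treated earlier whose readings are within limits would be coded as disease-free

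*Protocol*

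**What the plan says.** Under Method, Study population, the Protocol gives one criterion for each condition: "an AAA was defined as maximal infrarenal diameter of 30 mm or more, and PAD was defined as an ABI" outside two limits. The leg criterion in full is: "PAD was defined as an ABI < 0.90 or ≥ 1.40 using the same validated hand held Doppler-based methodology". The participants come from population-based screening trials and are aged 60 to 74.

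Under Statistics, these become outcomes: "Outcomes will be analyzed both as dichotomized variables, present CAC, severe CAC (CAC score above 400), AAA and PAD". The same sentence adds that they are also analysed "as the underlying continuous variables, CAC score, aortic diameter, and lowest measured ankle-brachial blood pressure index". The binary outcomes are therefore cut-offs applied to a screening measurement. The model for them is to "for each dichotomized outcome, estimate adjusted odds ratios using multivariable logistic regression, with cumulated noise pollution as exposure".

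Two other statements touch on earlier disease. Medical history appears as an example in a list of covariates: "Confounding CVD variables will be considered and adjusted for (e.g., lifestyle, medical history, QoL, weight" and so on. Register codes appear under Hypothesis: "The ICD or SKS disease classification code system will be used to identify clinical events for patients from the two trials". Neither is linked to AAA or PAD status at screening.

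**The concern.** The study aims at the prevalence as well as the incidence of cardiovascular disease. Someone whose aneurysm has been repaired, or whose leg circulation has been restored, has had the disease. After treatment the infrarenal diameter can be below 30 mm and the ABI can lie between the two limits. The stated definitions then place that person among the controls, and in the linear models the person contributes a diameter or ABI that reflects the treatment.

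Adjusting for medical history does not repair this, because the outcome is still coded as absent.

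What is at stake is the noise odds ratio for AAA and PAD. Treated disease may be more common among the more exposed. This could follow from the study's own hypothesis that exposure causes disease, or from socioeconomic differences in treatment. In either case, proportionally more true cases are removed from the exposed group and the association is weakened.

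**Working it through.** The Protocol gives no AAA or PAD prevalence, no treated share and no power figure for these models, so there is no figure of its own to reproduce. The first step is a reading of the text; the rest is illustration on assumed values.

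**Step 1: the text.** Trace a participant with an earlier aneurysm repair and a screening diameter below 30 mm.
- Study population: the criterion is not met, so there is no AAA.
- Statistics: the binary outcome is 0, and the measured diameter enters the linear model.
- Covariates: medical history may enter as a regressor; the outcome stays 0.
- Register codes: used for clinical events, not for status at screening.
- Exclusions: none stated for earlier treatment.

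The same path holds for a revascularised participant whose ABI is within limits.

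**Step 2: share of AAA cases missed (assumed inputs).** Missed share = repaired / (repaired + screen-detected). With 3% screen-detected and 0.3% to 1.0% repaired, this is 0.003/0.033 = 9% to 0.010/0.040 = 25%.

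**Step 3: effect on the odds ratio (assumed inputs).** Let true prevalence, treated cases included, be 3.75% in the less exposed and 4.5% in the more exposed. True OR = (0.045/0.955)/(0.0375/0.9625) = 1.21. If a share f of cases has been treated and reads as normal, observed prevalence = true prevalence × (1 − f). With f = 15% in the less exposed, observed prevalence there is 0.0375 × 0.85 = 3.19% and treated disease is 0.0375 × 0.15 = 0.56%.

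| f, more exposed | Observed prevalence, more exposed | Observed OR | Treated disease, more exposed | OR for treated disease |
|---|---|---|---|---|
| 15% | 3.83% | 1.21 | 0.68% | 1.20 |
| 17% | 3.74% | 1.18 | 0.77% | 1.36 |
| 20% | 3.60% | 1.13 | 0.90% | 1.61 |
| 25% | 3.38% | 1.06 | 1.13% | 2.01 |
| 30% | 3.15% | 0.99 | 1.35% | 2.42 |

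The last column shows what each row requires: how strongly exposure must be associated with treated disease for the observed OR to arise.

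**Step 4: precision when the treated share is equal.** Take the 33,723 participants in two equal exposure halves, true OR 1.20, two-sided alpha 0.05 (halves, OR and alpha assumed).
- Total prevalence 3%: missing 5%, 10% or 20% of cases loses about 51, 101 or 202 cases. The OR stays at about 1.20, and power falls from 0.81 to 0.79, 0.77 or 0.72.
- Total prevalence 10% (a PAD-like value): about 169, 337 or 674 cases are lost, and power stays above 0.99.

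**Step 5: unequal shares in the same set-up.** With 5% versus 10% treated, the OR of 1.20 is observed as about 1.13 at either prevalence. With 10% versus 20%, it is observed as 1.06 at 3% prevalence and 1.05 at 10%.

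**The case against.** The strongest reply is that the definition sentence only reports, in the past tense, the thresholds used by the parent trials. Rules for previously treated participants could sit in those trials' protocols or in a statistical analysis plan, neither of which is at hand. That stands as a limit: the documents cannot show that any treated participant is in fact a control. It does not remove the point. This Protocol fixes a definition, uses it for its own outcomes and refers to no further rule.

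Second, these are secondary analyses. The primary model is a Cox regression on mortality and cardiovascular morbidity, and the numbered hypotheses concern clinical disease. This stands.

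Third, not every treated participant reads as normal. A residual diameter may still be 30 mm or more. For PAD, the continuous variable is the lowest ABI measured; if PAD is coded from that value, a normal reading in a treated leg does not hide disease in the other. The event list under Hypothesis also names bypass separately from coronary bypass grafting, so some vascular procedures may already be extracted. These facts reduce the number affected, more for PAD than for AAA.

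Fourth, if the target is screening-detected disease, excluding treated participants is as defensible as counting them as cases. That is fair, and is why exclusion belongs among the sensitivity analyses. Neither choice leaves them as controls.

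A reader might go further and infer that the odds ratio could be pulled to or past 1, or that the analyses certainly lose the most severe cases. The documents support neither. On the assumed values, reaching 0.99 requires exposure to more than double treated AAA (OR about 2.4) while leaving untreated AAA unaffected, and nothing in the Protocol suggests that pattern. How many severe cases are lost is unknown.

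**Conclusion.** The point holds for the noise prevalence models. As written, AAA and PAD are determined by the screening reading alone, and treated participants with readings within limits are coded as disease-free. Adjusting for medical history does not undo this.

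The size cannot be obtained from the documents. With equal treated shares the bias is negligible and the loss is one of cases and modest power. With shares moderately higher among the exposed, the attenuation is small to moderate: 1.21 to about 1.18 or 1.13 in the illustration. Both results rest on assumed prevalences and treated shares, and on every treated case reading as normal, which overstates the effect.

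The primary Cox outcomes are not affected. The change is worth making because it is cheap and because counting these participants shows whether the problem is negligible.

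**What to change.** First confirm that the register extract covers procedures before the screening date; the Protocol does not say. Then:

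- Identify participants with a procedure code, dated before screening, for aortic aneurysm repair, lower-limb revascularisation or amputation for arterial disease.
- In the logistic models, define AAA as a diameter of 30 mm or more or an earlier repair, and PAD as the ABI criterion or an earlier leg procedure, so that these participants are never controls. Do not enter the same procedures as covariates in those models, since they would then be part of the outcome.
- Report how many participants are reclassified.
- As sensitivity analyses, give the screening-only definition and a version that excludes these participants.
- For the linear models of diameter and ABI, state that post-treatment readings reflect treatment, and report results with and without these participants. Exclusion alone should not be the only analysis: it selects on outcome severity and can itself attenuate the slope if treatment is related to exposure.

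The cost is a short code list applied to registers that are already to be used, a few sentences in the Protocol and some extra model runs. The downside is that the main case definition departs slightly from the parent trials' screening definition; the screening-only sensitivity analysis keeps that comparison available.
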